5.5 STRATEGIES FOR RECRUITMENT AND RETENTION

Phone calls to prospective patients will be made by site study coordinators who have been in touch with these same patients through the original HCMR study. All studies will be performed at the site that the patient was enrolled at in the original HCMR study.

6 STUDY INTERVENTION

6.1 STUDY INTERVENTION(S) ADMINISTRATION

6.1.1 STUDY INTERVENTION DESCRIPTION

A limited physical examination will be performed including heart rate and blood pressure Results of recent testing will be recorded including ECG, exercise testing, Holter monitoring, and echocardiography.

- Intravenous access will be obtained
- Blood draw (80 cc or approximately 5 tbsp.) for biomarkers, specimen banking and Hematocrit. No genetic testing will be performed.

Blood (80 cc or approximately 5 tablespoons) will be collected by peripheral venipuncture at enrollment as a source of serum and plasma for biomarker analysis. Fasting samples are requested but if this is not possible logistically, non-fasting samples can be acquired and noted as such.

A urine sample will be collected, as applicable, to determine pregnancy status.

Full details of the protocol will be in the Blood Draw Manual

• CMR

A CMR will be performed and will take approximately one hour. 0.15mM of gadolinium contrast will be infused through an intravenous line during the MRI. Full details of the protocol will be in the Imaging Manual.

6.1.2 DOSING AND ADMINISTRATION n/a

6.2 PREPARATION/HANDLING/STORAGE/ACCOUNTABILITY

6.2.1 ACQUISITION AND ACCOUNTABILITY n/a

6.2.2 FORMULATION, APPEARANCE, PACKAGING, AND LABELING $\ensuremath{\mathsf{n/a}}$

6.2.3 PRODUCT STORAGE AND STABILITY n/a

6.2.4 PREPARATION n/a

6.3 MEASURES TO MINIMIZE BIAS: RANDOMIZATION AND BLINDING

n/a

6.4 STUDY INTERVENTION COMPLIANCE

n/a

6.5 CONCOMITANT THERAPY

6.5.1 RESCUE MEDICINE n/a

7 STUDY INTERVENTION DISCONTINUATION AND PARTICIPANT DISCONTINUATION/WITHDRAWAL

7.1 DISCONTINUATION OF STUDY INTERVENTION

n/a

7.2 PARTICIPANT DISCONTINUATION/WITHDRAWAL FROM THE STUDY

The patients are able to withdraw from the study at any point in time.

7.3 LOST TO FOLLOW-UP

Patients lost to f/u will be accounted for. They will be considered lost to follow-up if they do not respond to 3 phone calls and a certified letter. Should there be substantial losses additional sites can be added, as only a fixed number of patients per site can be recruited based on the strict entry criteria.

8 STUDY ASSESSMENTS AND PROCEDURES

8.1 EFFICACY ASSESSMENTS

n/a. No therapy is being studied and thus efficacy is not addressed.

8.2 SAFETY AND OTHER ASSESSMENTS

The patient will be monitored by MRI staff and the CRC during the CMR from the control room. Blood pressure and heart rate will be monitored during the MRI. A few patients will have devices (pacer or implantable cardioverter-defibrillator) and this will increase the needed ECG monitoring by device nurse or MRI staff. These devices will need to be interrogated by a device nurse prior to the MRI scan, adjusted to the proper setting for MRI, and then reset after the scan.

8.3 ADVERSE EVENTS AND SERIOUS ADVERSE EVENTS

8.3.1 DEFINITION OF ADVERSE EVENTS (AE)

AN AE IS ANY UNTOWARD MEDICAL OCCURRENCE IN A SUBJECT UNDERGOING THE INITIAL STUDY PROCEDURES.8.3.2 DEFINITION OF SERIOUS ADVERSE EVENTS (SAE)

An SAE is any untoward medical occurrence that:

- Results in death.
- Is life-threatening. Any adverse experience that places the subject, in the view of the investigator, at immediate risk of death from the reaction as it occurred (i.e., it does not include a reaction that, had it occurred in a more serious form, might have caused death).
- Requires in-patient hospitalization or prolongation of existing hospitalization.
- Results in persistent or significant disability or incapacity.
- Is a congenital anomaly/birth defect.
- An event that required intervention to prevent permanent impairment or damage..

8.3.3 CLASSIFICATION OF AN ADVERSE EVENT

8.3.3.1 SEVERITY OF EVENT

Mild, moderate, severe

8.3.3.2 RELATIONSHIP TO STUDY INTERVENTION

Related or unrelated to the study

8.3.3.3 EXPECTEDNESS

Expected or unexpected

8.3.4 TIME PERIOD AND FREQUENCY FOR EVENT ASSESSMENT AND FOLLOW-UP During and immediately after the CMR and blood draw

8.3.5 ADVERSE EVENT REPORTING

Adverse events that are not serious will not be reported in this study.

8.3.6 SERIOUS ADVERSE EVENT REPORTING

Adverse events that are deemed to be serious, related and unexpected will be reported to each site's local IRB.

8.3.7 REPORTING EVENTS TO PARTICIPANTS

Reporting events to participants will occur on necessary basis.

8.3.8 EVENTS OF SPECIAL INTEREST

n/a

8.3.9 REPORTING OF PREGNANCY

pregnancy testing will be required for women of childbearing potential as pregnant patients will be excluded.

8.4 UNANTICIPATED PROBLEMS

8.4.1 DEFINITION OF UNANTICIPATED PROBLEMS (UP) Any other adverse event that is not expected

8.4.2 UNANTICIPATED PROBLEM REPORTING To the IRB

8.4.3 REPORTING UNANTICIPATED PROBLEMS TO PARTICIPANTS As necessary

9 STATISTICAL CONSIDERATIONS

9.1 STATISTICAL HYPOTHESES

• Primary Efficacy Endpoint(s):

n/a

• Secondary Efficacy Endpoint(s):

9.2 SAMPLE SIZE DETERMINATION

n/a

9.3 POPULATIONS FOR ANALYSES

All patient data collected

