3 OBJECTIVES AND ENDPOINTS

OBJECTIVES	ENDPOINTS	JUSTIFICATION FOR ENDPOINTS
Primary		
To assess the change in LGE extent from baseline over a minimum of 7 years of follow-up extent in HCM patients who would have been candidates for clinical trials of aficamten.	Change in % LGE mass	LGE extent is a risk factor for SCD. The progression of LGE over time is incompletely understood.
Secondary		
To assess the change in CMR parameters including LV mass, volumes, and maximal wall thickness, from baseline over a minimum of 7 years of follow-up extent in HCM patients who would have been candidates for clinical trials of aficamten.	LV mass, end-diastolic volume (EDV), end-systolic volume (ESV), stroke volume (SV), ejection fraction (EF), and LV mass index (I), EDVI, ESVI, SVI RV EDV, ESV, SV, EF, EDVI, ESVI, SV, EF Maximal wall thickness LV and RV longitudinal, circumferential, and radial strain LGE – presence, mass T1 – regional and global Extracellular volume – regional and global LA volume, LAVI, and LA strain	Prior f/u CMR studies in HCM are short-term and with a small n. This would be the largest f/u study to date with the largest n.
Tertiary/Exploratory		
To assess the change in biomarkers from baseline over a minimum of 7 years of follow-up extent in HCM patients who would have been candidates for clinical trials of aficamten.	NTproBNP and hsTNT and change in these measures from baseline	Changes in biomarkers over time are also important to understand in HCM

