5 STUDY POPULATION

5.1 INCLUSION CRITERIA

Patients in the original HCMR cohort with:

1) Obstructive HCM

- Males and females between 18 and 65 years of age
- BMI < 35 kg/m2
- LVOT-G at entry as follows:

Resting gradient ≥50 mmHg OR Resting gradient ≥30 mmHg and <50 mmHg with post-Valsalva LVOT-G ≥50 mmHg

• NYHA Class II or III

or

2) Non-obstructive HCM

- Same criteria as above except resting LVOT-G is <30mmHg and post-Valsalva gradient <50mm Hg
- BMI <40kg/m2
- Elevated NT-proBNP > 300 pg/mL at the time of enrollment
- LVEF ≥55%

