5.4 SCREEN FAILURES

Patients who have died or been lost to follow-up since entry into the original study

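### The analysis pools patients who had septal reduction or, rarely, transplant between the two scans with everyone else, so procedural change can be read as LGE progression.

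*Protocol*

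**What the plan says.** Protocol Section 3 gives the primary endpoint as "Change in % LGE mass" and justifies it on the ground that "The progression of LGE over time is incompletely understood". LV mass and maximal wall thickness are among the secondary endpoints there.

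Section 4.1 plans to approach 314 patients, 187 obstructive and 127 non-obstructive, first scanned in 2014-17. Section 5.1 selects the obstructive group on NYHA class II or III and on the outflow gradient: "Resting gradient ≥50 mmHg OR Resting gradient ≥30 mmHg and <50 mmHg with post-Valsalva LVOT-G ≥50 mmHg".

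Sections 5.2 and 5.4 mention neither septal reduction nor transplant. The only exclusions in Section 5.2 that clearly act at the time of re-imaging are pregnancy and pacemaker dependence. Section 5.4 adds "Patients who have died or been lost to follow-up since entry into the original study".

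Section 9.3 then defines the analysis population in full as "All patient data collected". Section 9.4.2 describes absolute and percent change from baseline and looks at associations with baseline values. Section 9.4.3 relates the changes to clinical outcomes. Sections 9.4.7 (sub-groups) and 9.4.9 (exploratory analyses) are marked n/a. The schedule of activities in Section 1.3 includes a medical history at the single visit, but no analysis draws on it.

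**The concern.** Septal reduction acts on the tissue that the endpoints measure. Alcohol ablation leaves a septal infarct that enhances as LGE. Myectomy takes out septal muscle, so LV mass and maximal wall thickness fall at once. A transplanted patient would have a donor heart compared with the native heart scanned at baseline.

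The group most exposed to septal reduction is also the larger of the two, because it was chosen for high gradients and symptoms. A site following the protocol scans these patients, and their change goes into the primary result with no flag. Since the endpoint is justified by the wish to understand LGE progression, a reader will take the pooled mean as disease progression when part of it may be procedural. Section 9.4.3 carries the problem forward: scar made by a procedure could appear as prognostic progression when change is related to outcomes.

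**Working it through.** **Is there any route by which these patients leave the analysis?** Reading Sections 5.1, 5.2, 5.4, 9.3, 9.4.2, 9.4.3, 9.4.7 and 9.4.9 together, there is none. Eligibility rests mainly on status at original entry. The later grounds are pregnancy, pacemaker dependence, death and loss to follow-up. Pacemaker dependence may remove some ablation patients, but not as a class.

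**Inputs from the protocol (Section 4.1).** 187 + 127 = 314, which reproduces the stated total. Obstructive share: 187 / 314 = 59.6%.

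**Inputs that are assumed.** The protocol gives no procedure rate and no effect per procedure. Let f be the share of obstructive patients with the procedure between scans and d the change it causes per patient.

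- Shift in the obstructive mean = f × d
- Shift in the pooled mean = 187 × f × d / 314

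**Ablation and % LGE**, f = 5% to 15% (about 9 to 28 patients), d = +4 to +10 percentage points:

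- Pooled, low: 187 × 0.05 × 4 / 314 = +0.12 points
- Pooled, high: 187 × 0.15 × 10 / 314 = +0.89 points
- Obstructive only: 0.05 × 4 = +0.2 to 0.15 × 10 = +1.5 points

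With a smaller effect of +2 to +5 points at the same rates, the pooled shift is 187 × 0.05 × 2 / 314 = +0.06 to 187 × 0.15 × 5 / 314 = +0.45 points.

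**Myectomy and LV mass**, f = 10% to 30% (about 19 to 56 patients), d = -15 to -40 g:

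- Pooled, low: 187 × 0.10 × (-15) / 314 = -0.9 g
- Pooled, high: 187 × 0.30 × (-40) / 314 = -7.1 g
- Obstructive only: 0.10 × (-15) = -1.5 g to 0.30 × (-40) = -12 g

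**Myectomy and % LGE.** Write % LGE as L / M, with L the enhanced mass and M the LV mass. Removing r grams of muscle that contain s grams of LGE gives (L - s) / (M - r). This falls if s / r exceeds L / M and rises if it is smaller. The protocol gives nothing to decide between them, so the sign is open.

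**Transplant.** One patient going from 5% or 20% LGE to zero moves a mean of 314 by -5 / 314 = -0.016 or -20 / 314 = -0.064 points.

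**Denominator.** 314 is the number to be approached, not the number scanned. The pooled shifts hold for the scanned set only if take-up is similar in obstructive and non-obstructive patients, with and without a procedure.

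**The case against.** The strongest reply is that the protocol never promises natural change. Its objective reads "To assess the change in LGE extent from baseline over a minimum of 7 years of follow-up extent in HCM patients", in people who would have qualified for aficamten trials. Change under usual care, procedures included, is a coherent target for a descriptive study with no hypothesis test and no sample size calculation. This stands: a reader might infer that the protocol targets procedure-free disease progression, but it does not say so. What it does give is an observational design and an endpoint justified by LGE progression, and the pooled figure alone cannot answer that question. If usual-care change is meant, the protocol should say so.

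A second reply is that events between scans can be left to a statistical analysis plan, and that n/a in this template need not be a ban, since exploratory analyses are n/a although Section 3 lists an exploratory objective. This carries some weight. But Section 9.3 is not silent: it names everyone as the population, and no other section separates these patients.

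Third, a reader might infer that the pooled result is uninterpretable. The protocol does not support that. It gives no SD or expected change against which to judge the shift, the low end of the assumed range is about +0.1 points, and Section 9.4.1 plans medians and interquartile ranges beside means, which limit the pull of a minority of extreme values.

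Fourth, making a procedure-free set the only primary set would condition on an event after baseline and describe only patients who did not have a procedure. This is a fair objection, and it argues for showing the results side by side.

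**Conclusion.** The point holds, and the plan should be changed, although the flaw does not invalidate the study. As written, patients with septal reduction between scans are analysed together with the rest, in a cohort where 187 of 314 were selected for symptomatic obstruction.

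The case on the primary endpoint rests on ablation scar, with an assumed pooled shift of about +0.1 to +0.9 points of % LGE. For LV mass it rests on myectomy, with an assumed shift of about -0.9 to -7.1 g. Wall thickness falls too, but no size can be given. All rates and effects are assumptions, so the true bias is unknown; opposing effects may partly cancel in the mean while widening the spread.

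Two stronger readings should be avoided. Myectomy cannot be said to lower % LGE, because it changes both numerator and denominator. Transplant belongs in the rule for completeness, but on these figures a single case barely moves the mean.

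**What to change.** - **Data:** in the medical history already scheduled, record septal reduction, transplant and any other procedure that scars or removes LV myocardium, with type and date.
- **Sections 9.3 and 9.4.2:** pre-specify that change in LGE, LV mass, wall thickness, strain, T1 and ECV is reported (a) for patients with a native heart and no such procedure between scans, as the estimate to be read as disease progression; (b) for procedure patients as a separate group, with number, type and change; and (c) for all patients.
- **Section 9.4.3:** apply the same separation to the associations with clinical outcomes.

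The cost is wording in three sections and one dated field on an existing form, with no extra visit or scan. The drawback is that set (a) is smaller, mainly among obstructive patients, and represents only those who had no procedure; the all-patient result is kept beside it for that reason. The rule should be fixed before change data are seen, so that the choice of set cannot follow the results.

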9.4 STATISTICAL ANALYSES

9.4.1 GENERAL APPROACH

CMR, echocardiographic parameters and biomarkers will be described by means and standard deviations, medians and interquartile ranges for continuous variables, minimum and maximum values and counts and percentages for categorical variables.

9.4.2 ANALYSIS OF THE PRIMARY EFFICACY ENDPOINT(S)

Change from baseline to follow-up CMR, echocardiographic and biomarkers will be described by absolute difference (follow-up value minus baseline value) and percent change from baseline((follow-up value – baseline value)/baseline value x 100). Associations with baseline values will be examined.

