4 STUDY DESIGN

4.1 OVERALL DESIGN

A total of 314 patients from 9 sites (187 with oHCM, 127 with nHCM) will be approached to consent for re-imaging and repeat blood draw. Patients will be approached by the individual site PI and/or CRC and all studies will be performed at that site. Patients who consent will undergo a repeat CMR with similar a protocol to that performed as per the initial study in 2014-17. The only substitution would be a wideband sequence for LGE imaging in patients with devices, as available.

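### Mean percent change in NT-proBNP and hsTnT is above zero with no true change unless entry selected on the marker; report a geometric mean ratio by subtype

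*Protocol*

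**What the plan says.** Section 9.4.2 names two change measures for all imaging and biomarker variables. The first is the raw difference: "Change from baseline to follow-up CMR, echocardiographic and biomarkers will be described by absolute difference (follow-up value minus baseline value". The second is "percent change from baseline((follow-up value – baseline value)/baseline value x 100". Neither 9.4.2 nor any other section names a ratio or log-scale measure.

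Section 9.4.1 says that CMR, echocardiographic and biomarker variables are "described by means and standard deviations, medians and interquartile ranges for continuous variables", with minimum and maximum as well. Means and medians stand side by side with no order of preference.

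The Section 3 table places "NTproBNP and hsTNT and change in these measures from baseline" at the tertiary/exploratory level. Section 9.4.3 says that associations between these changes and clinical outcomes will be examined, without giving a scale or model.

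Section 5.1 requires, for nHCM only, "Elevated NT-proBNP > 300 pg/mL at the time of enrollment". There is no such rule for oHCM, and no rule on hsTnT in either group.

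**The concern.** NT-proBNP and hsTnT are positive markers whose within-person variation is better described by ratios than by differences. Percent change with the baseline as divisor is asymmetric for such a marker: it can rise without limit but cannot fall below -100%. Averaging it turns pure fluctuation into an apparent rise, and recruiting more patients does not remove the effect.

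The interval is long ("To assess the change in biomarkers from baseline over a minimum of 7 years of follow-up extent in HCM patients"), and fasting state may differ between visits, since "non-fasting samples can be acquired and noted as such". Some within-person variation is therefore to be expected, although the protocol does not say how much. At stake is whether a mean rise in a marker can be read as disease progression when a stable group would show the same figure.

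**Working it through.** The protocol gives no biomarker SD, expected change or sample-size calculation (9.2 is marked not applicable), so there is no stated figure to reproduce. The check asks what each summary would show if nothing had changed.

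**Inputs from the protocol.** The percent-change formula (9.4.2), the summary statistics (9.4.1), the numbers to be approached ("A total of 314 patients from 9 sites (187 with oHCM, 127 with nHCM", Section 4.1), and the NT-proBNP rule for nHCM (5.1).

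**Assumed, not in the protocol.** The SD s of log(follow-up/baseline), taken as 0.3 to 1.0. For the nHCM simulation, also a total log SD of 1.0 or 1.3 and a source-population median of 200, 300 or 600 pg/mL.

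**Step 1: two patients.** One goes from 300 to 600 and one from 600 to 300. The percent changes are +100% and -50%, with mean (100 - 50)/2 = +25%. The mean log ratio is (ln 2 + ln 0.5)/2 = 0.

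**Step 2: no selection on the marker.** If log(follow-up/baseline) is normal with mean 0 and SD s, then:

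- mean percent change = 100 × (exp(s²/2) - 1)
- median percent change = 0
- geometric mean ratio = 1, a change of 0%

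At s = 0.5, exp(0.125) - 1 = 13.3%. The direction does not depend on lognormality. If baseline B and follow-up F are exchangeable, E[F/B] = E[B/F], and the average of F/B and B/F is never below 1.

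**Step 3: size against sampling error.** The SD of percent change is 100 × √((exp(s²) - 1) × exp(s²)): 32.1 at s = 0.3 and 60.4 at s = 0.5. If all 187 oHCM patients take part, the standard error at s = 0.5 is 60.4/√187 = 4.4, so the false rise is 13.3/4.4, about 3.0 standard errors. At s = 0.3 it is about 2.0. For hsTnT over all 314 patients, the figures are 2.5 at s = 0.3 and 3.9 at s = 0.5.

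**Step 4: NT-proBNP in nHCM.** Pairs were simulated with no true change (2 million per scenario), keeping those with baseline above 300 pg/mL. The ranges below run over the assumed medians and total SDs.

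| s | No selection: mean % change | No selection: median and geometric mean change | nHCM NT-proBNP: mean % change | nHCM NT-proBNP: geometric mean change |
|---|---|---|---|---|
| 0.3 | +4.6 | 0 | -0.5 to +2.8 | -1.7 to -4.8 |
| 0.5 | +13.3 | 0 | -1.5 to +7.8 | -4.6 to -12.6 |
| 0.7 | +27.8 | 0 | -3.8 to +15.4 | -8.9 to -23.1 |
| 1.0 | +64.9 | 0 | -12.0 to +31.1 | -17.3 to -41.4 |

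In this group, two errors of opposite sign meet in the mean percent change. The log ratio removes the asymmetry and leaves regression to the mean. The median falls in the same way (-4.6% to -12.6% at s = 0.5).

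**Step 5: pooling NT-proBNP at s = 0.5.** The mean percent change is (187 × 13.3 + 127 × m)/314 with m from -1.5 to +7.8, which gives about +7% to +11%. The pooled geometric mean change is about -2% to -5%. A pooled figure mixes the two effects and describes neither group.

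**The case against.** The strongest reply is that the protocol already prescribes a robust summary. The median percent change is 0 under no change where there is no selection, and a clearly positive mean beside a median near 0 reveals the skew. That stands: the fault lies in one of two prescribed summaries, not in percent change as such. It does not save the mean, because the protocol gives the two equal standing.

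It can also be said that 9.4.2 attaches no summary statistic to the change measures and that log transformation belongs in the SAP. The mean percent change does come from reading 9.4.1 and 9.4.2 together. That is the natural reading, and the percent-change formula is written out, so an SAP that follows the protocol would carry it over. The point concerns a stated method, not missing detail.

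Three stronger readings are tempting, and the protocol does not support them:

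- A reader might infer that both biomarkers will show a false rise in both groups. For NT-proBNP in nHCM, 127 of 314 patients (40%), the entry rule can bring the mean to zero or below.
- A reader might infer that a log ratio cures the problem everywhere. In that group it still shows a fall with no true change, and at s = 0.5 it can lie further from zero than the mean it replaces.
- A reader might infer that the skewed percent change is the predictor in 9.4.3. That section fixes no scale.

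Finally, the consequence is limited. Section 3 makes the endpoint tertiary. The synopsis does mention biomarkers in its primary objective, but its primary endpoint is LGE mass, and no hypothesis or decision rests on biomarker change.

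**Conclusion.** The point holds in a limited form. For hsTnT in both groups and NT-proBNP in oHCM, the mean percent change that follows from 9.4.1 and 9.4.2 is above zero when nothing has changed: +4.6% at s = 0.3, +13.3% at s = 0.5 and +64.9% at s = 1.0. The median stays at 0. For NT-proBNP in nHCM the same asymmetry is present but is offset partly or wholly by regression to the mean, so the sign of the mean is not assured.

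This rests on four assumptions:

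- The value of s, which the protocol does not give. The direction in the unselected cases is firm; the size is not.
- The source-population median and spread used for nHCM.
- Enrollment in the NT-proBNP rule means entry to the original registry. If it means the re-imaging visit, the selection effect runs the other way; Section 5.1 does not settle this.
- The remaining entry criteria do not themselves select on transient values of the marker in question.

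This is a free improvement to a tertiary, descriptive endpoint. It is not an error that threatens the primary result.

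**What to change.** In 9.4.2, for NT-proBNP and hsTnT only:

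- Replace the mean and SD of percent change with the geometric mean ratio: the mean of log(follow-up/baseline) with its 95% CI, back-transformed and, if wished, expressed as a percentage.
- Keep medians and IQRs.
- Report oHCM and nHCM separately.
- State that NT-proBNP change in nHCM is subject to regression to the mean from the entry cut-off, and that the log ratio does not remove it. Say at which visit the cut-off was applied.

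In 9.4.3, use the log ratio if biomarker change serves as a predictor.

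The cost is wording in the protocol or SAP. No added data, visits or samples are needed.
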